8.8. Classification of an adverse event (seriousness, severity, causality, expectedness)

It is important that the investigator gives his/her own opinion regarding the **seriousness**, the **intensity** of the event as well as the **cause-effect relationship** between an AE and the research (IMP, NIMP or study protocol). This evaluation must be assessed by the investigator and reported in the AE form. In addition, the sponsor will be responsible for the evaluation the **expectedness** of the event (Section 8.9.3).

The Seriousness should be evaluated according to international guidance (see definition Section 8.4, in accordance with International Council for Harmonisation of Technical Requirements for Pharmaceuticals for Human Use (ICH) Topic E2A³³ and EU DIRECTIVE 2001/20/EC of 4 April 2001.³⁴

The severity of all AEs will be graded according to the NCI-CTCAE on a five-point scale (Grade 1 to 5) (version 5.0):

- Grade 1: Mild; asymptomatic or mild symptoms; clinical or diagnostic observations only; intervention not indicated.
- Grade 2: Moderate; minimal, local or non-invasive intervention indicated; limiting age-appropriate instrumental activities of daily living (ADL)¹.
- Grade 3: Severe or medically significant but not immediately life-threatening; hospitalization or prolongation of hospitalization indicated; disabling; limiting self-care ADL².
- Grade 4: Life-threatening consequences; urgent intervention indicated.
- Grade 5: Death related to AE.

The cause-effect relationship

The investigator must make an assessment in the AE form whether the AE is related or not to the research, meaning:

- AE related to IMP(s).
- AE related to study protocol *i.e.* related to:
 - A procedure scheduled in the study protocol (*i.e.* exercise test, MRI, etc.), or
 - A change or withdrawal of previous / concomitant treatment related to the conditions of the protocol or
 - A product other than the IMP, taken as part of the protocol (NIMP or other).

¹ *Instrumental Activities of Daily Living (ADL) refer to preparing meals, shopping for groceries or clothes, using the telephone, managing money, etc.*

² *Self-care ADL refer to bathing, dressing and undressing, feeding self, using the toilet, taking medications, and not bedridden.*

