8.9.3. Responsibilities of the sponsor

In accordance with international guidance, the assessment of the seriousness and the causality of adverse events are usually made by the investigator but falls also under sponsor's duties, who is responsible for ensuring that all suspected unexpected serious adverse reactions are reported to Competent Authorities and Ethics Committees.

The sponsor will review the seriousness of the adverse events and the causality of (at least) the serious adverse events, whether reported by the investigator or upgraded by the sponsor. The causality and the seriousness may be upgraded (but never downgraded). Anonymized copies of relevant documents may be asked for the event assessment. If the assessments of the investigator and the sponsor are different, both will be reported in the clinical study report.

In addition, the sponsor is responsible for determining whether an AE is **expected or unexpected**. An AE will be considered unexpected if the nature, severity, or frequency of the event is not consistent with the risk information previously described for the IMP.

Independently of the regulatory obligations of the investigator, the sponsor must report the pharmacovigilance data and any new safety finding likely to affect the benefit /risk balance of the product, required in ICH GCP guidelines and local regulations, to the appropriate Authorities, to all the investigators involved and to the trial participants involved - through the investigators - as mentioned in [Section 13.4](#).

The concerned authorities will be notified as soon as possible by the sponsor of the DMC recommendations if any, where relevant for the safety of subjects (*i.e.* modification or termination of the study).

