10.1.2.6.1. Adverse events

Treatment-emergent adverse events are defined as any AEs reported from the date of first administration of IMP to 30 days after the last date of IMP. Frequency and percentages of participants will be summarized for: any grade TEAE, Grade 3 or higher TEAE, IMP related TEAE, serious TEAE, TEAE leading to dose modification, TEAE leading to IMP discontinuation, death and TEAE leading to death. Adverse events will be summarized by SOC and preferred term. All AE data will be listed by participant.

Of note, the seriousness and the relationship to the IMP of the adverse event correspond to the investigator opinion or, in case of events upgraded by the sponsor for seriousness or for causality in case of SAE, to the sponsor opinion.

Number and percentage of participants who experienced a DLT will be summarized and listed for Safety Lead-In part.

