7.1. Adverse events

Each **medical concept of adverse events coded according to the internal "multiple medical concept" process** is taken into account as a single adverse event in the statistical analysis.

The modalities of the adverse event (onset and end dates, severity, seriousness, action taken, additional therapy, relationship, outcome...) replicated by default to each medical concept are also taken into account in the statistical analyses.

Emergent adverse events on treatment are defined as all adverse events:

- Which occur between the first IMP intake date (included) and the last IMP intake date "+ 30 days" (included), considering the definition of last study drug intake defined in [Section 5.1.5](#)

or

- Which occur before the first IMP intake date and which worsen (in terms of severity) or become serious according to the investigator opinion between the first IMP intake date (included) and the last IMP intake date "+ 30 days" (included), considering the definition of last study drug intake defined in [Section 5.1.5](#).

Note: Adverse events occurring or worsening or becoming serious on the day of the first study drug/associated agent intake (if any) is considered as emergent.

Serious adverse events are defined from investigator assessment as all adverse events fulfilling at least one of the following seriousness criteria for immediate notification: death, hospitalisation or prolongation of hospitalisation, medically important, life-threatening, disability/incapacity or congenital anomaly.

A fatal adverse event corresponds to an adverse event with "Fatal" as outcome.

Adverse events related to Trifluridine/tipiracil correspond to adverse events associated with the answer "Related" to the "Is this event related to Trifluridine/tipiracil" question.

Adverse events related to Futuximab/modotuximab correspond to adverse events associated with the answer "Related" to the "Is this event related to Futuximab/modotuximab" question.

Adverse events related to the combination correspond to adverse events associated with the answer "Related" to the "Is this event related to Trifluridine/tipiracil" question and/or with the answer "Related" to the "Is this event related to Futuximab/modotuximab" question.

Adverse events related to disease progression correspond to adverse events associated with the answer "Related" to the "Is this event related to disease progression" question.

The following information will be taken into account:

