- For the analyses where the severity of the adverse event is considered, the worst severity from the day of emergence and during the studied period (*i.e.* between the first study drug/associated agent intake date (included) and the last study drug/associated agent intake date (as defined in [Section 5.1.5](#)) “+ 30 days” (included) will be taken into account.
- The number of patients by worst grade: for each patient, system organ class and preferred term, we analyze the worst grade of events.
- The number of events by worst grade: for each patient, system organ class and preferred term, we analyse the worst grade of each event. The percentage will be calculated as the number of events of the PT concerned at grade X divided by the total number of events of the PT concerned.
- For the analyses where the action taken regarding the study drug and the additional therapy requirement are considered, all the actions taken and additional therapy requirements recorded from the day of emergence and on the studied period will be taken into account.
- However, in case of an episode of an emergent adverse event leading to studied treatment withdrawal reported after the last study drug/associated agent intake date (as defined in [Section 5.1.5](#)) “+ 30 days”, the adverse event will be considered as leading to studied treatment withdrawal during the studied period.
- Seriousness is judged by event: if one episode is serious (whatever the time it occurs), the whole event will be considered as serious.
- A severe adverse event corresponds to an adverse event with NCI CTCAE grade 3, 4 or 5.
- Any grade corresponds to an adverse event with NCI CTCAE grade 1, 2, 3, 4 or 5.
- All multicoded events will be taken into account in the analyses.
- For the analysis of recovered emergent adverse event during / after treatment period, a TEAE is considered as recovered “during treatment period” (“after end of treatment period”, respectively) if the associated outcome is “recovered” or “recovered with sequelae” and occurs between the first study drug/associated agent intake date and the last study drug/associated agent intake date (as defined in [Section 5.1.5](#)) “+ 30 days” (included) (strictly after the last study drug/associated agent intake date (as defined in [Section 5.1.5](#)) “+ 30 days”, respectively).

The following rules are applied in case of missing severity:

Table (7.1) 1 - Treatment-emergence of adverse events in case of missing severity/grade (if any)

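### SAP 7.1 takes seriousness of adverse events from the investigator alone, whereas protocol 10.1.2.6.1 uses the sponsor's opinion for events the sponsor upgraded

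*SAP*

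**What the plan says.** Protocol 10.1.2.6.1 sets the rule for the adverse event analysis. Seriousness and relationship to the IMP follow the investigator or, "in case of events upgraded by the sponsor for seriousness or for causality in case of SAE, to the sponsor opinion". The source of upgrades is protocol 8.9.3: "The sponsor will review the seriousness of the adverse events and the causality of (at least) the serious adverse events". That section allows upgrading, rules out downgrading, and requires both opinions in the clinical study report where they differ.

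SAP 7.1 states the seriousness rule differently. Serious adverse events "are defined from investigator assessment as all adverse events fulfilling at least one of the following seriousness criteria". The SAP also treats a pre-dose event as treatment-emergent if, on treatment, it worsens or has "become serious according to the investigator opinion" as its route to emergence. Seriousness is judged by event: "if one episode is serious (whatever the time it occurs), the whole event will be considered as serious".

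On relationship, SAP 7.1 names no assessor. For example, "Adverse events related to Futuximab/modotuximab correspond to adverse events associated with the answer" Related to the question about that drug; trifluridine/tipiracil is handled in the same way. SAP 3.5.1 lists the outputs that use these definitions: serious TEAEs, non-serious TEAEs, and related TEAEs leading to death.

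**The concern.** Protocol Table (3.4) 1 makes the incidence, severity and relationship of TEAEs and serious TEAEs a primary endpoint of the Safety Lead-In. The randomised part is cancelled, and SAP 1.1 keeps only the primary analysis and best overall response, so the safety tables are most of what will be reported.

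The two documents give different answers on which opinion feeds those tables when investigator and sponsor disagree on seriousness. The difference runs one way. A programmer following the SAP as written would put a sponsor-upgraded event in the non-serious table, which SAP 3.5.1 labels as the EudraCT analysis. The protocol would put the same event in the serious table.

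**Working it through.** The plan gives no figure to reproduce. The check is a comparison of texts, followed by the size of one reclassification.

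1. **Seriousness.** Take an event that the investigator calls non-serious and the sponsor upgrades. Under protocol 10.1.2.6.1 it is analysed as serious. Under SAP 7.1 it does not meet the definition. No other part of the supplied SAP restores the upgrade rule, and the version 2.0 change list does not mention it.

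2. **Direction.** The sponsor can only add serious events (protocol 8.9.3). For a given emergence definition, the serious events under the SAP are a subset of those under the protocol. So:
   - serious TEAE counts are equal or lower under the SAP;
   - non-serious TEAE counts are equal or higher;
   - related-serious counts are equal or lower. An event the investigator called related, and the sponsor upgraded for seriousness alone, drops out of related-serious whatever is done about causality.

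3. **Condition on a shift.** Because SAP 7.1 makes the whole event serious if any episode is, an event moves from serious to non-serious only if no episode of it was serious in the investigator's assessment.

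4. **Size.** The input is n, the number in the Safety Set (SAP 2.1: anyone with at least one IMP dose). A participant counted in a row only through an upgrade changes that row by 1/n.
   - Planned n of about 25: 1/25 = 4.0 percentage points.
   - Assumed values, for range only: 1/6 = 16.7, 1/12 = 8.3, 1/20 = 5.0, 1/30 = 3.3 points.
   - No upgrades, or a participant already in the row through another event: 0.

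   The final n is not stated. The study stopped during the Lead-In, so n may be below 25. Participants replaced as not DLT-evaluable stay in the Safety Set, so n may also exceed the DLT-evaluable count.

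5. **Causality.** Protocol 10.1.2.6.1 carries sponsor causality upgrades for SAEs only. Protocol 8.8 says of the assessment that includes causality: "This evaluation must be assessed by the investigator and reported in the AE form". This suggests that the Related answer is the investigator's, but the SAP does not say what the analysis variable holds after sponsor review. SAP 3.5.1 refers the reader to Appendix D on relationship, and that appendix is the quality-of-life section, marked not applicable. The SAP therefore leaves open whether causality upgrades are carried.

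6. **Emergence.** The protocol's TEAEs are "defined as any AEs reported from the date of first administration of IMP to 30 days after the last date of IMP", with no provision for pre-dose events that become serious. The SAP's extra condition therefore has no protocol rule to conflict with, which is why step 2 holds the emergence definition fixed.

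**The case against.** Several points against the concern have force.

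- **It may already be declared.** The SAP's change-log footnote says the version 1.0 entry lists changes from the protocol. No version 1.0 entry is visible in the supplied copy, and text just before the version 2.0 entry was not available. A reader might infer an undeclared departure; the documents do not support that.
- **Protocol version.** SAP section 1 cites the amended protocol of 16 August 2022. The supplied amendment log ends at version 3.0 of 26 July 2022. The comparison assumes 10.1.2.6.1 is the same in both.
- **Causality.** A reader might infer that the SAP excludes sponsor causality upgrades. It does not say so, and its silence is compatible with the protocol rule.
- **Multi-episode events.** A reader might infer that every uncarried upgrade reclassifies an event. It does not if another episode was already serious to the investigator.
- **Consequence.** Both opinions must appear in the study report where they differ, so the information is not lost. The analysis is single-arm and descriptive. DLT counts are unaffected, because protocol 4.1.3.2 ties DLT relatedness to the investigator.

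These points limit the finding but do not remove it. Reporting both opinions does not settle which one feeds the primary tables; the protocol settles that, and the SAP's seriousness definition departs from it. If the database already merges upgrades, the SAP wording is wrong and still needs correcting.

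**Conclusion.** The conflict on seriousness holds. As written, SAP 7.1 can only leave serious and related-serious counts equal to or below those under protocol 10.1.2.6.1, and non-serious counts equal or above, for a given emergence definition. The actual size is unknown because no upgrade count is given: 0 with no upgrades, and 4.0 points per participant counted only through an upgrade if n is 25.

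The causality question is a secondary gap in the SAP, not a contradiction. If causality upgrades were not carried, a fatal event judged related only by the sponsor could be absent from the related-TEAE-leading-to-death table. A reader might infer that such a death would disappear from the report. It would not: a fatal TEAE stays in the TEAE-leading-to-death table, and the death stays in the SAP 3.5.2 listing.

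The conclusion rests on 10.1.2.6.1 being unchanged in the protocol version the SAP cites. A deviation declared in SAP version 1.0 cannot be excluded. The sponsor should correct the wording or confirm the declaration.

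**What to change.** - In SAP 7.1, define seriousness as the investigator's opinion or, where the sponsor upgraded the event, the sponsor's. Apply this to the serious and non-serious TEAE tables of SAP 3.5.1.
- For SAEs, state that relationship to each IMP follows the same rule, including in the related-TEAE-leading-to-death table, and say whose answer the Related variable holds.
- For internal consistency, use the same seriousness definition in the SAP's own emergence condition for pre-dose events that become serious. The protocol has no rule for that condition.
- If investigator-only is intended and not already declared, declare it as a change from the protocol.

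The cost is SAP wording, merging assessments the sponsor must already make under protocol 8.9.3, and re-running the affected tables if they have been produced. No new data are collected. Serious and related-serious counts may rise and non-serious counts may fall.

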3.4. Endpoints

The study endpoints for the Safety Lead-In and Randomised parts are listed in [Table \(3.4\) 1](#) and [Table \(3.4\) 2](#) respectively.

Table (3.4) 1 - Endpoints for the Safety Lead-In Part

	Objectives	Endpoints
Primary	To assess safety and tolerability of futuximab/modotuximab in combination with trifluridine/tipiracil according to National Cancer Institute Common Terminology Criteria for Adverse Events (NCI-CTCAE) v5.0	
 - Incidence of dose-limiting toxicities (DLTs) - Incidence, severity and relationship of Treatment Emergent Adverse Events (TEAEs) and Serious Treatment Emergent Adverse Events (STAEs) - AEs leading to dose interruption, modification, delays and permanent treatment stop - Changes from baseline in key laboratory safety assessments, and vital signs

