Severity/Grade		Adverse event considered as	
Nearest before the first study drug/associated agent intake date	During the study period		
Missing	Missing	→	Treatment-emergent
Missing	Grade 1	→	Non treatment-emergent
Missing	Grade 2, 3, 4 or 5	→	Treatment-emergent
Grade 1, 2, 3	Missing	→	Treatment-emergent
Grade 4	Missing	→	Non treatment-emergent

CL3-95026-001 - Statistical Analysis Plan | VV-TMF-130355 | 1.0

The rules for substitution of missing or incomplete episode date (onset date, dates of the six seriousness criteria and dates of change of severity and action taken) are as follows:

Table (7.1) 2 - Substitution rules of AE dates

Date to substitute	Substituted date (Episode date)
../mmm/yyyy	If same month and year than first study drug/associated agent intake date then: First study drug/associated agent intake date Else: 01/mmm/yyyy
•/yyyy	If same year than first study drug/associated agent intake date then: First study drug/associated agent intake date Else: 01/JAN/yyyy
•/....	First study drug/associated agent intake date

Note: ..mm/yyyy = missing day
..../yyyy = missing day and month
..../.... = missing date

The rules for substitution of missing or incomplete recovery dates, in case of AE outcome "recovered" or "recovered with sequelae" are as follows:

Table (7.1) 3 - Substitution rules of recovery date

Date to substitute	Substituted date
../mmm/yyyy	If same month and year than date of AE last information ^(*) then: Date of AE last information Else: Last day of the month /mmm/yyyy
..../yyyy	If same year than date of AE last information ^(*) then: Date of AE last information Else: 31/DEC/yyyy
..../....	Date of AE last information^(*)

Notes:
- ..mm/yyyy = missing day,
..../yyyy = missing day and month,
..../.... = missing date.

^(*) Date of AE last information is defined as the maximum between onset date, dates of change of severity and action taken and dates of the six seriousness criteria for this adverse event.

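### SAP Table (7.1) 2 can date a worsening or a treatment action before the adverse event began, and SAP 7.1 read literally then leaves it out of the worst-grade and action-taken tables

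*SAP*

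**What the plan says.** SAP 7.1, Table (7.1) 2, sets the substitution rule for a "missing or incomplete episode date (onset date, dates of the six seriousness criteria and dates of change of severity and action taken". All of these dates are handled alike:

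- Day missing: "If same month and year than first study drug/associated agent intake date then: First study drug/associated agent intake date Else: 01/mmm/yyyy"
- Day and month missing: "If same year than first study drug/associated agent intake date then: First study drug/associated agent intake date Else: 01/JAN/yyyy"
- Whole date missing: the "first study drug/associated agent intake date"

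No line of the table refers to the onset of the event concerned.

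Earlier in SAP 7.1, the window for severity is "the worst severity from the day of emergence and during the studied period". For treatment actions, "all the actions taken and additional therapy requirements recorded from the day of emergence and on the studied period will be taken into account". One exception widens the action rule, and it covers only withdrawals reported more than 30 days after the last intake. Seriousness has its own rule: "if one episode is serious (whatever the time it occurs), the whole event will be considered as serious".

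Protocol Table (3.4) 1 lists the severity of TEAEs, and "AEs leading to dose interruption, modification, delays and permanent treatment stop", among the primary endpoints of the Safety Lead-In. SAP 3.5.1 tabulates TEAEs by worst grade and by action taken.

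**The concern.** Taking the earliest possible date is cautious for onset, because it favours calling the event treatment-emergent. It is not cautious for a later milestone of the same event. It can produce an impossible sequence, in which a worsening or a dose change comes before the event exists. A program that follows the emergence condition to the letter then discards that record. The event stays in the tables, but at a lower worst grade or without the action.

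The randomised part was cancelled. SAP 1.1 keeps only the primary analysis and best overall response, so the safety tables are the main output of the study.

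**Working it through.** The plan states no figure on this point, so there is none to reproduce. The check applies Table (7.1) 2 literally and compares the result with a known onset date.

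**Worked dates**

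1. First IMP 10 January; Grade 2 onset 15 March; Grade 3 and dose reduced, both dated March with the day missing. March is not the month of first IMP, so both become 1 March, 14 days before onset. Read literally, worst grade stays 2 and no reduction is counted.
2. First IMP 12 September; onset 20 September; true worsening 27 September, day missing. The substituted date is 12 September, 8 days before onset.
3. As in 2, but with the true worsening on 5 October. The substituted date is 1 October, after onset, and the record is kept.

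**When the substituted date precedes onset** (onset on treatment and fully dated)

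- Wholly missing: the result is the first IMP date, which precedes every onset after the first IMP day.
- Day and month missing, same year as onset: the result is the first IMP date or 1 January, which precedes onset unless onset was on that very day.
- Day missing, same month as onset: the result is the first IMP date or the 1st, with the same qualification. If the change falls in a later month than onset, the 1st of that month is after onset and nothing is lost.

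**How often, given a partial date**

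Take the day-missing case with a change L days after an onset on day d of a month of M days. The date precedes onset for d = 2 to M − L, which is M − (L + 1) days. The share is therefore about 1 − (L + 1)/30.44, or zero if that is negative, using the month length in SAP 5.1.3.

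A simulation of 40,000 events per scenario gives the ranges below. Its assumptions are not in the documents: first IMP dates spread over one year, onset uniform over 56 or 198 days from first IMP, and onset fully dated. The 198 days are the Synopsis figure of about 6.5 months of treatment, 6.5 × 30.44 = 197.9.

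| L (days) | Day missing, formula | Day missing, simulated | Day and month missing | Wholly missing |
|---|---|---|---|---|
| 1 | 0.934 | 0.917–0.928 | 0.977–0.990 | 0.982–0.996 |
| 3 | 0.869 | 0.854–0.864 | 0.971–0.984 | 0.982–0.995 |
| 7 | 0.737 | 0.725–0.734 | 0.961–0.972 | 0.982–0.994 |
| 14 | 0.507 | 0.499–0.507 | 0.942–0.954 | 0.982–0.995 |
| 28 | 0.047 | 0.049 | 0.906–0.914 | 0.982–0.995 |
| 56 | 0 | 0 | 0.829–0.838 | 0.982–0.995 |

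The wholly-missing column agrees with 1 − 1/56 = 0.982 and 1 − 1/198 = 0.995, because only onset on the first IMP day escapes.

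**Where nothing is lost**

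If onset is missing to the same degree in the same month, both dates receive the same value and the record stays in.

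**Effect on a rate**

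1/25 = 4 percentage points for one participant, if 25 are analysed.

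**The case against.** The strongest reply is that the loss depends on one reading. The severity rule is followed by a parenthesis running from first intake to last intake plus 30 days, and dates substituted for on-treatment events never fall before first intake. The emergence condition has an obvious purpose: to exclude pre-treatment grades of events that began before treatment and later worsened. The rules on counting by worst grade carry no date condition of their own. A sensible programmer might therefore never discard such a record.

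This shows that the loss is not certain. But the parenthesis explains the studied period and does not cancel the emergence condition. The action rule has no such parenthesis. The worst-grade rules say what is counted and do not reset the window. A rule that two programmers could apply differently still needs the missing sentence.

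Four stronger readings are tempting, and the documents do not support them:

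- A reader might infer that serious status is lost too, since seriousness dates share the table. It is not, because SAP 7.1 judges seriousness per event regardless of timing.
- A reader might infer that nearly every partial date falls before onset. With only the day missing, the share is about half at 14 days and about 5% at 28 days.
- A reader might infer that the error runs only one way. Suppose last intake plus 30 days is 10 March, onset is in February, and a worsening on 20 March is recorded without its day. It becomes 1 March and is counted although it lies outside the window.
- A reader might infer a 4-point shift per partial date. The shift needs the lost record to be that participant's only qualifying event, and the final number of participants is not given.

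Related data also make a hidden omission less likely. DLTs have a dedicated form (Protocol 4.1.3.3), trifluridine/tipiracil dose reductions come from the dispensing page (SAP 5.2.1.4), withdrawal reasons appear in disposition (SAP 5.2.1.1), and data validation can raise queries (Protocol 14.2). None of these replaces the adverse-event tables by worst grade or action taken.

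**Conclusion.** The rule is wrong as written. Table (7.1) 2 can place a severity change or a treatment action before the onset of its own event, and it usually does so in the three situations set out above. Read literally, SAP 7.1 then leaves the record out of tables that feed primary Safety Lead-In endpoints. The main risk is understated worst grade and treatment actions, with an occasional error the other way.

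The conclusion assumes an on-treatment onset that is fully dated, or at least dated more precisely than the later milestone, and a literal application of the emergence condition. The documents do not say how many dates are incomplete, so the actual effect is unknown and may be nil.

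**What to change.** Add one sentence under Table (7.1) 2. The onset date is substituted first, as now. For an incomplete severity-change or action-taken date, the substituted date is then max(Table (7.1) 2 date, AE onset date). Seriousness dates need no change to protect serious status.

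Do not cap the result at a substituted recovery date. Table (7.1) 3 derives recovery from the latest of these same dates, so the cap would be circular. A cap is safe only where the recovery date is fully recorded.

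The cost is one sentence and one line of code. By construction, no substituted severity-change or action-taken date then precedes onset, and the cautious onset rule is untouched. If the tables have already been run, a listing of records whose substituted date precedes onset would show whether any was dropped.
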